urine) laboratory	Screening	for a creatinine (serum or urine) laboratory test.
testing		
TB screening	Outcome:	Defined as ≥1 procedure code or ≥1 ICD-10 diagnosis code
•	Screening	for TB (active and latent) screening.
	Outcome:	
	Monitoring	
Viral hepatitis B and C	Outcome:	Defined as ≥1 procedure code or ≥1 ICD-10 diagnosis code
screening	Screening	for viral hepatitis B and C screening.
-	Outcome:	
	Monitoring	
Absolute lymphocyte	Outcome:	Defined as ≥1 procedure code or ≥1 ICD-10 diagnosis code
count (ALC)	Screening	for ALC laboratory testing.
laboratory testing	Outcome:	
	Monitoring	
Absolute neutrophil	Outcome:	Defined as ≥1 procedure code or ≥1 ICD-10 diagnosis code
count (ANC)	Screening	for ANC laboratory testing.
laboratory testing	Outcome:	
	Monitoring	
Haemoglobin	Outcome:	Defined as ≥1 procedure code or ≥1 ICD-10 diagnosis code
laboratory testing	Screening	for haemoglobin laboratory testing.
	Outcome:	
	Monitoring	
Alanine	Outcome:	Defined as ≥1 procedure code or ≥1 ICD-10 diagnosis code
aminotransferase	Screening	for ALT and/or AST laboratory testing.
(ALT) and/or	Outcome:	
Aspartate	Monitoring	
aminotransferase		
(AST) laboratory		
testing		

Table 3. Operational definitions of study variables in Système National des Données de Santé

Variable	Role	Operational definition
Lipid panel (i.e., total	Outcome:	Defined as ≥1 procedure code or ≥1 ICD-10 diagnosis code
cholesterol, high-	Monitoring	for lipid panel laboratory testing.
density lipoprotein		
(HDL), low-density		
lipoprotein (LDL) and		
triglycerides (TG))		
laboratory testing		
Describe prescribing p	atterns over time: De	scribe changes in the utilisation of tofacitinib following the
		or use after the 2019 Article 20 referral, the 2021 signal
evaluation procedure,	and the 2022/2023 JA	Ki Article 20 referral
Adherence to recomme	endations for limitation	ons of use in patients with VTE risk factors (will be
stratified by VTE repo	rting period 1, 2, 3)	
Assessment of VTE risk	factors prior to initiati	on of tofacitinib
Prior VTE	Outcome: changes	Defined as ≥1 ICD-10 diagnosis code for VTE in the 12
	in use in patients	months prior to the index tofacitinib dispensing.
	with VTE risk	List of VTE codes in ANNEX 12. LIST OF DIAGNOSIS
	factors	CODES FOR VTE.
History of surgery,	Outcome: changes	Defined as ≥1 procedure code for a major surgery in the
major	in use in patients	3 months prior to the index tofacitinib dispensing.
	with VTE risk	
	factors	

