ANNEX 10. LIST OF LABORATORY TEST CODES

Laboratory test	Label (French)	Biology code
Creatinine (serum	CLAIRANCE (RENALE) DE LA CREATININE	0407
or urine)	PROFIL ENZ PANCREATIQUE	1531
	(AMYLASEMIE+AMYLASÜRIE+EVENT CREATININEMIE)	
	SANG: CREATININE	0592
	SANG : UREE ET CREATININE	0593
	UR. : CREATININE (CREATININURIE)	0627
TB screening	MYCOBACTERIES : IDENTIF. BIOCH AUTRE QUE	0244
	MYCOBACTERIUM TUBERCULOSIS	
	MYCOBACTERIES: IDENTIFICATION BIOCHIMIQUE DE	0243
	MYCOBACTERIUM TUBERCULOSIS	
Viral hepatitis B	HEPATITE B (VHB) : SD : AC ANTIHBC IGM PAR EIA	0352
and C screening	HEPATITE B (VHB) : SD : AC ANTIHBC TOTAUX PAR EIA	0351
8	HEPATITE B (VHB) : SD : AC ANTIHBE PAR EIA	0354
	HEPATITE B (VHB) : SD : AC ANTIHBS (IGG OU IG TOTALES)	0323
	PAR EIA	0020
	HEPATITE B (VHB) : SD : AG HBE PAR EIA	0353
	HEPATITE B (VHB): SD: AG HBS PAR EIA	0322
	HEPATITE B (VHB): CONTROLE DE GUERISON	4712
	HEPATITE B (VHB): DEPISTAGE ET/OU DIAGNOSTIC	4500
	HEPATITE B (VHB): DEPISTAGE ET/OU DIAGNOSTIC IGM ANTI	4501
	HBC	7501
	HEPATITE B (VHB): GENOME (ADN) (VHB): HYBRIDATION	4120
	MOLECULAIRE	7120
	HEPATITE B (VHB): STATUT IMMUNITAIRE DANS LE CADRE	4714
	D'UNE VACCINATION.	7/17
	HEPATITE B (VHB): SUIVI D'UNE HEPATITE B CHRONIQUE	4711
	HEPATITE B (VHB): SURVEILLANCE DE LA GROSSESSE	4715
	HEPATITE B (VHB): SORVEILEANCE DE LA GROSSESSE HEPATITE B (VHB):SD CONTROLE AVANT VACCINATION:AC	4713
	ANTI HBS+AC ANTI HBC EIA	4/13
	HEPATITE B (VHB):SD INFECTION RECENTE:AG HBS+AC	4710
	ANTI-HBC IGM PAR EIA	4/10
	GENOME (ARN) VIRUS DE L'HEPATITE C (VHC) : HYBRID	4121
	MOLEC: DETECTION QUALITATIVE	4121
	GENOME (ARN) VIRUS DE L'HEPATITE C (VHC): HYBRID	4123
	MOLEC: DETECTION QUALITATIVE	4123
	HEPATITE C (VHC): DETECTION QUANTITATIVE GENOME	4124
	(ARN)	4124
	HEPATITE C (VHC): GENOTYPAGE DU VHC PAR BIOLOGIE	4125
	MOLECULAIRE	4123
		2705
	HEPATITE C (VHC) : SD DE CONTROLE	3785
	HEPATITE C (VHC) : SD DE DEPISTAGE : AC ANTI-VHC	3784
Haemoglobin	ELECTROPHORESE DE L'HEMOGLOBINE (CITRATE AGAR)	1114
laboratory testing	ELECTROPHORESE DE L'HEMOGLOBINE (GEL	1113
	POLYACRYLAMIDE) HEMOGRAMME Y COMPRIS PLAQUETTES (NFS , NFP)	1104
	HEMATOCRITE (HTE)	2108

Laboratory test	Label (French)	Biology
		code
Alanine	ALANINE AMINOTRANSFERASE (ALAT,TGP) (SANG)	0516
aminotransferase	ASPARTATE AMINOTRANSFERASE (ASAT,TGO)(SANG)	0517
and/or aspartate	TRANSAMINASES (ALAT ET ASAT, TGP ET TGO)(SANG)	0522
aminotransferase		
laboratory testing		
(i.e., liver function		
testing)		
Lipid panel (i.e.,	SANG: CHOLESTEROL TOTAL (CHOL)	0580

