total cholesterol,	SANG: CHOLESTEROL-LDL (C-LDL)	2001
high-density	SANG: TRIGLYCERIDES (TG)	0590
lipoprotein [HDL],		
low-density		
lipoprotein [LDL]		
and triglycerides		
[TG]) laboratory		
testing		

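### The at-least-one-code rule lets a test for one virus count as hepatitis B and C screening, and one lipid analyte count as a full lipid panel, so reported adherence on these two outcomes may be overstated

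*Protocol*

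**What the plan says.** Table 3 gives the laboratory screening and monitoring outcomes one common form: "Defined as ≥1 procedure code or ≥1 ICD-10 diagnosis code", followed by the test. For hepatitis the test is a single combined variable, "for viral hepatitis B and C screening", with both a screening and a monitoring role. For lipids it is a single monitoring variable, "for lipid panel laboratory testing", whose label names four components: total cholesterol, HDL, LDL and triglycerides. ALC and ANC are separate variables with both roles; the first is worded "for ALC laboratory testing". Table 3 refers to Annex 10 for the codes.

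Annex 10 has one row for hepatitis B and C together. It includes entries such as "HEPATITE B (VHB): SUIVI D'UNE HEPATITE B CHRONIQUE" (4711). The lipid row has three codes, for total cholesterol (0580), LDL (2001) and "SANG: TRIGLYCERIDES (TG" (0590). The haemoglobin row includes "ELECTROPHORESE DE L'HEMOGLOBINE (CITRATE AGAR" (1114) and "HEMOGRAMME Y COMPRIS PLAQUETTES (NFS , NFP" (1104). There is no row for ALC or ANC.

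Two passages leave work to the SAP. Section 9.3.1 calls the algorithms and codes preliminary and open to refinement. Section 9.9.1.2 says laboratory procedure codes will be identified and confirmed with the database owner and local clinicians, and that a test without a code will be noted.

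**The concern.** Two outcomes are labelled as composites of several tests but scored on any one of them. A patient tested for hepatitis B and never for hepatitis C is counted as screened for both. A patient with one triglyceride measurement is counted as having had a four-component panel.

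Adherence to screening and laboratory monitoring is a named part of primary objective 2 (Section 8). Section 7 says the study's data will help to judge whether the risk minimisation materials are effective. An error that can only raise adherence leans towards a favourable answer.

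**Working it through.** The Protocol states no figure for laboratory adherence, so there is none to reproduce. The check is a count of codes followed by set arithmetic.

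**Step 1: codes in Annex 10.**

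| Outcome | Codes listed | Count |
|---|---|---|
| Hepatitis B only | 0352, 0351, 0354, 0323, 0353, 0322, 4712, 4500, 4501, 4120, 4714, 4711, 4715, 4713, 4710 | 15 |
| Hepatitis C only | 4121, 4123, 4124, 4125, 3785, 3784 | 6 |
| Covering both viruses | none | 0 |
| Lipids, single analyte | 0580, 2001, 0590 | 3 |
| HDL, or a combined lipid code | none | 0 |
| ALC, ANC | none | 0 |

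Because no code covers both viruses, any one of the 21 hepatitis codes meets the combined variable while documenting only one virus.

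**Step 2: direction.** Let B and C be the proportions with at least one code for each virus in a window. Then

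- any code = B + C − both;
- overstatement = any code − both = B + C − 2 × both.

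The overstatement is the proportion tested for exactly one virus. It is zero or positive, never negative. The same holds for lipids: the proportion with any component is never below the proportion with all of them.

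**Step 3: illustrative size.** The testing rates are assumptions; the documents give none.

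| Assumed B, C | Overlap | Any code | Both | Gap (points) |
|---|---|---|---|---|
| 80%, 60% | nested | 80% | 60% | 20 |
| 80%, 60% | independent | 1 − 0.2 × 0.4 = 92% | 0.8 × 0.6 = 48% | 44 |
| 80%, 60% | least possible | 100% | 80 + 60 − 100 = 40% | 60 |
| 90%, 80% | nested | 90% | 80% | 10 |
| 90%, 80% | least possible | 100% | 70% | 30 |
| 60%, 60% | always ordered together | 60% | 60% | 0 |

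For lipids, assume triglycerides 70%, total cholesterol 60% and LDL 50%:

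- nested: any code 70%, all three 50%, a gap of 20 points;
- independent: any code 1 − 0.3 × 0.4 × 0.5 = 94%, all three 0.7 × 0.6 × 0.5 = 21%, a gap of 73 points.

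HDL cannot be counted with the listed codes under any of these assumptions.

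**The case against.** The strongest reply is that this is code-list work left to the SAP. Sections 9.3.1 and 9.9.1.2 do cover most questions about individual codes: the missing ALC and ANC rows, the missing HDL code, the electrophoresis entries, and the hepatitis entries labelled follow-up, recovery check or genotyping. That part of the reply stands. It does not reach the counting rule, which is in Table 3. Adding or removing codes does not turn at least one into one of each.

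A second reply is that the labels join their components with a conjunction, so all may be intended. The Protocol does use and/or for ALT and AST, and or for the hepatitis comorbidity, where one suffices. That supports a both-viruses intention, but then the stated rule does not carry it out. At the least, Table 3 needs to say which is meant.

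A third reply is that these outcomes are only described and tabulated (Section 9.7.2.2), with no formal comparison or sample size depending on them. This is true and limits the weight of the point. The tabulated proportion is still the result that will be read.

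A reader might also infer more than the documents support:

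- **ALC and ANC adherence will be reported as 0% or misstated.** Section 9.9.1.2 says a test without a code will be noted. As listed, the two are not derivable, which is a different problem.
- **The blood count code 1104 already supplies ALC and ANC.** Its Annex 10 label mentions platelets and no differential, so this needs confirmation.
- **Follow-up and similar hepatitis codes are plainly wrong.** The variable also has a monitoring role, where such codes may belong.

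**Conclusion.** The point holds for hepatitis and lipids. Under the rule in Table 3 and the rows in Annex 10, one component satisfies an outcome named for several, so adherence against the all-components definition may be overstated and cannot be understated.

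The size depends on how often the tests are ordered separately, which the documents do not give. At assumed rates of 80% and 60% the hepatitis gap runs from 20 to 60 points, with 44 under independence; it is zero if the tests always go together. A reader might take 20 to 44 points as the expected error, but it is neither an estimate nor a bound.

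The remaining Annex 10 questions are items to settle when the code list is finalised, not errors in reported adherence.

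**What to change.** **In Table 3, hepatitis:** require at least one HBV code and at least one HCV code. Report HBV, HCV and both, in each window and over the whole 180-day pre-index span. The wider span keeps patients whose two tests fall in different windows from being lost.

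**In Table 3, lipids:** report each component and all components, with any lipid test as a second line. Either add an HDL code or drop HDL from the label.

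**When Annex 10 is finalised with the database owner and clinicians:**

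- check whether 4711, 4712 and 4125 belong in the pre-initiation screening outcome;
- check whether 1113 and 1114 belong under haemoglobin;
- add ALC and ANC rows, using 1104 if it is confirmed to include the differential.

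**Cost:** edits to Table 3 and Annex 10, a few more output lines, and possibly a few added codes in the extraction. Section 9.7 says major changes to primary endpoint definitions would be reflected in a protocol amendment, so the rule is best settled before analysis. Reported hepatitis and lipid adherence may be lower.

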Finally, in July 2018, tofacitinib 5 mg tablet BID and 10 mg tablet BID were approved by the EC for the treatment of moderately-to-severely active ulcerative colitis (UC) in patients with inadequate response, loss of response or intolerance to conventional therapy or a biologic agent. UC is a bowel disease characterised by inflammation and ulcers in the colon and rectum. In clinical trials, patients treated with 5 mg or 10 mg of tofacitinib BID were more likely to achieve and/or maintain a clinical response and remission of their condition as compared to patients in the placebo group.³ At the time of initial approval, the doses of tofacitinib for the treatment of moderately-to-severely active UC were 10 mg BID for induction (up to a 16-week period) and 5 mg BID for maintenance, which should not be exceeded.⁴

Table 1 summarises the date to facitinib was approved by the EC and the approved dose for each of the 3 approved indications.

Table 1. Summary of approved indications and dosages for tofacitinib

Indication	Date approved by the EC	Approved dose
RA	March 2017	5 mg immediate-release tablets BID
	December 2019	11 mg prolonged-release tablets QD
PsA	June 2018	5 mg immediate-release tablets BID
	July 2021	11 mg prolonged-release tablets QD
UC	July 2018	5 mg and 10 mg immediate- release tablets BID

Note: BID is an abbreviation for "bis in die," which in Latin means twice a day; QD is an abbreviation for "quaque die," which in Latin means once a day

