In May 2019, the EC requested a reassessment of the benefit-risk of tofacitinib pursuant to Article 20 of Regulation (EC) No 726/2004 due to a signal for increased risks of pulmonary embolism (PE) and mortality arising in an ongoing Pfizer-sponsored Phase 3b/4 safety study (A3921133: Phase 3b/4 Randomized Safety Endpoint Study of 2 Doses of Tofacitinib in Comparison to A Tumor Necrosis Factor (TNF) Inhibitor in Subjects with Rheumatoid Arthritis) designed to evaluate the risk of malignancy and major adverse cardiac events in RA patients aged 50 years and older who had at least one cardiovascular (CV) risk factor. In November 2019, the Committee on Human Medicinal Products (CHMP) concluded that, based on a recommendation from the Pharmacovigilance Risk Assessment Committee (PRAC), patients treated with tofacitinib are at increased risk of venous thromboembolism (VTE) events, both for deep vein thrombosis (DVT) as well as PE, especially in patients with risk factors for VTE. The PRAC further concluded that the risk of VTE events is dosedependent. To minimise this risk, the PRAC recommended that warnings be added to the Summary of Product Characteristics (SmPC) regarding the increased risk of VTE observed in patients taking tofacitinib, especially for patients with known risk factors for VTE. The PRAC also recommended that treatment with tofacitinib be discontinued in patients with suspected VTE and that tofacitinib 10 mg BID for maintenance treatment is not recommended in patients with UC who have known VTE risk factors, unless there is no suitable alternative therapy available. Clarifications on the posology were also added, particularly for UC patients in maintenance. Specifically, some patients (i.e., patients who failed to respond to alternative treatment options for UC such as TNF inhibitor treatment) who had a reduction in response to 5 mg BID maintenance treatment may benefit from an increase in maintenance dose to 10 mg BID; for these patients, the presence of known risk factors for VTE should be considered. However, to facitinib 10 mg BID for maintenance treatment should be used for the shortest duration possible.⁴

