no use of an		Note: This definition will miss those who have one 10 mg
alternative therapy		BID prescription and the remaining prescriptions are 5 mg
(i.e., biologic) prior to		BID.
tofacitinib initiation		
A patient who has	Outcome:	Among UC patients, is defined as ≥ 1 prescription dispensing
known VTE, CV or	Adherence to	for a biologic (as identified by ATC codes) prior to the index
malignancy risk	recommended	tofacitinib dispensing and an ADD >10 mg in any of the
factors with an ADD	posology	intervals: Weeks 17-24, Weeks 25-32, Weeks 33-40 or
of >10 mg in Weeks		Weeks 41-48 of follow-up and ≥1 VTE, CV or malignancy
17-24, Weeks 25-32,		risk factors from baseline to Week 16.
Weeks 33-40 or		
Weeks 41-48 of		An ADD \geq 15 mg in the definition above will be used in a
follow-up and with		sensitivity analysis.
evidence of a		
diagnosis for UC but		
no use of an		
alternative therapy		
(i.e., biologic) prior to		
tofacitinib initiation		

Adherence to patient screening and laboratory monitoring prior to and during tofacitinib treatment

The following recommended screenings and monitoring will be assessed in the following time frames:

- In the 30 days prior to and including the day of tofacitinib initiation;
- In the 31 to 60 days prior to tofacitinib initiation;

Table 3. Operational definitions of study variables in Système National des Données de Santé

Donnees de Sante			Donnees	
	Variable	Role		Operational definition

- In the 61 to 90 days prior to tofacitinib initiation; and
- In the 91 to 180 days prior to tofacitinib initiation;

For patients with at least 6 months of tofacitinib therapy (duration of tofacitinib therapy defined in Section 9.3.2):

- In the 60 days after the day of tofacitinib initiation;
- In the 61 to 120 days after tofacitinib initiation; and
- In the 121 to 180 days after to facitini binitiation.

For patients with 12 months of tofacitinib therapy (duration of tofacitinib therapy defined in Section 9.3.2):

- In the 181 to 240 days after tofacitinib initiation;
- In the 241 to 300 days after to facitinib initiation; and
- In the 301 to 360 days after to facitinib initiation.

For analyses, 1 month will be defined as 30 days and 1 year will be defined as 360 days.

List of laboratory codes in ANNEX 10. LIST OF LABORATORY TEST CODES.

List of laboratory codes	III THI TILL TO. LIDT	OF EMBORITORY TEST CODES.
Creatinine (serum or	Outcome:	Defined as ≥1 procedure code or ≥1 ICD-10 diagnosis code

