Initiating tofacitinib with ≥1 VTE risk factor(s)	Outcome: changes in use in patients with VTE risk factors	Defined as ≥1 VTE risk factor(s) (as listed and defined above) identified in the 12 months prior to the index tofacitinib dispensing.
Initiating tofacitinib with ≥1 VTE risk factors other than CV or malignancy risk factors	Outcome: changes in use in patients with VTE risk factors	The same definition as above but only limited to VTE risk factors other than CV or malignancy risk factors.
VTE risk factor scores	Outcome: changes in use in patients with VTE risk factors	Calculated as the sum of the number of VTE risk factors (as listed and defined above) identified in the 12 months prior to the index tofacitinib dispensing. Weighting of VTE risk factors may be considered as a sensitivity analysis to reflect the potential different
Number of UC patients with: ≥1 VTE risk factor; no prior alternative therapy (i.e., biologic); and an ADD >10 mg in Weeks 17-24, Weeks 25-32, Weeks 33-40 or Weeks 41-48 of follow-up	Outcome: changes in use in patients with VTE risk factors	importance of each risk factor. Defined as an UC patient meeting all of the following criteria: ≥1 VTE risk factor(s) (as listed and defined above) 12 months prior to the index tofacitinib prescription dispensing; 0 prescription medication dispensing for a biologic (as identified by ATC codes) in the 12 months prior to the index tofacitinib prescription dispensing; and an ADD of >10 mg in any of the intervals: Weeks 17-24, Weeks 25-32, Weeks 33-40 and Weeks 41-48 of follow-up (ADD defined in Section 9.3.3). Complete list of biologics in ANNEX 7. LIST OF ATC CODES FOR MEDICATIONS OF INTEREST TO AVOID WHILE TAKING TOFACITINIB.
Assessment of VTE risk; Section 9.3.2)	factors while receiving	tofacitinib therapy (duration of tofacitinib therapy defined in
VTE	Outcome: changes in use in patients with VTE risk factors	Defined as ≥1 ICD-10 diagnosis code for VTE while receiving tofacitinib therapy. List of VTE codes in ANNEX 12. LIST OF DIAGNOSIS CODES FOR VTE

Table 3. Operational definitions of study variables in Système National des Données de Santé

Variable	Role	Operational definition
Surgery, major	Outcome: changes in use in patients with VTE risk factors	Defined as ≥1 procedure code for a major surgery while receiving tofacitinib therapy.
MI	Outcome: changes in use in patients with VTE risk factors	Defined as ≥1 ICD-10 diagnosis code for an MI while receiving tofacitinib therapy.

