9.7.2.4.1. Patients with venous thromboembolism risk factors

To describe changes in the utilisation of tofacitinib, this analysis will be stratified by the VTE reporting periods 1, 2 and 3.

The proportion of patients with one or more risk factors for VTE, identified prior to tofacitinib initiation, will be described and tabulated overall and by individual VTE risk factor (e.g., prior VTE and recent MI).

Logistic regression analyses will be used to calculate odds ratios along with their corresponding 95% confidence intervals and p values to formally compare the proportion of patients with VTE risk factors across VTE reporting periods 1, 2 and 3.

To enhance statistical power in detecting changes, a composite score for the VTE risk factors will also be generated by summing the individual VTE risk factors. Linear regression analyses will be employed to compare the VTE composite score across the VTE reporting periods. In addition to the summed composite score, the same analysis using a composite score weighting the risk factors may be considered in an exploratory fashion (weights will be developed and described in the SAP). Regression coefficients with their 95% confidence intervals and p values will be generated.

The proportion of patients diagnosed with UC, one or more VTE risk factors identified prior to tofacitinib initiation and no use of alternative therapy (i.e., biologic) prior to tofacitinib initiation whose ADD in Week 17 through Week 24, Week 25 through Week 32, Week 33 through Week 40 or Week 41 through Week 48 was >10 mg will be described and tabulated.

The proportion of patients who discontinue or continue to facitinib after developing one or more VTE risk factors while taking to facitinib will be described separately.

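### The UC maintenance-dose outcome by VTE period fixes VTE risk status at index, while its sibling dose rows count risk factors to Week 16

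*Protocol*

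**What the plan says.** Section 7 of the Protocol gives the recommendation being measured: "tofacitinib 10 mg BID for maintenance treatment is not recommended in patients with UC who have known VTE risk factors", unless no suitable alternative exists. For patients who failed other options and whose response falls on 5 mg BID, it allows a higher maintenance dose and adds that "for these patients, the presence of known risk factors for VTE should be considered". Maintenance follows "10 mg BID for induction (up to a 16-week period").

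The outcome for this recommendation is a row of Table 3 (Section 9.3.1), under the heading for VTE factors before initiation. It requires a UC patient to have "≥1 VTE risk factor(s) (as listed and defined above) 12 months prior to the index tofacitinib prescription dispensing", no biologic in those 12 months, and ADD above 10 mg in at least one 8-week interval of Weeks 17–48. Section 9.7.2.4.1 repeats the condition as "one or more VTE risk factors identified prior to tofacitinib initiation and no use of alternative therapy (i.e., biologic") and splits by VTE reporting period.

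Two other Table 3 rows use risk factors with the same threshold and intervals. The posology row takes VTE, CV or malignancy "risk factors from baseline to Week 16". The JAKi-referral row uses the same window for CV or malignancy factors.

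**The concern.** The dose is judged from Week 17, but risk status is frozen up to 16 weeks earlier. The recommendation concerns maintenance treatment, so the factors that matter are those known when the maintenance dose is chosen. A biologic-naive UC patient with no factor before index may start hormonal therapy or have major surgery during induction and then stay above 10 mg/day. That is the use the recommendation advises against, yet the VTE row does not count the patient.

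At stake is an undercount of non-adherent use in the one firmly planned outcome that joins UC maintenance dose, VTE risk and VTE period. The VTE row is also not comparable with its siblings. The plan gives no reason for the different window.

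**Working it through.** The plan gives no numerical figure for this outcome, so there is none to reproduce. The check is mainly a comparison of text.

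**1. The three rows side by side**

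| Row | Factors | Window | Prior biologic | ADD | Split |
|---|---|---|---|---|---|
| VTE row (Table 3; Section 9.7.2.4.1) | VTE | 12 months before index (3 for major surgery and MI) | None | >10 mg, Weeks 17–48 | VTE period |
| Posology row (Table 3; Section 9.7.2.1) | VTE, CV or malignancy | Baseline to Week 16 | None by label; at least one by definition | Same | None stated |
| JAKi row (Table 3; Section 9.7.2.5.1) | CV or malignancy | Baseline to Week 16 | Either | Same | JAKi period |

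**2. Does another outcome flag the patient?** Take a biologic-naive UC patient with a first VTE factor in Weeks 1–16 and ADD above 10 mg afterwards.

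- Posology row: the label would count the patient. The definition cell would not, since it reads "Among UC patients, is defined as ≥ 1 prescription dispensing" of a biologic. Under either reading, Section 9.7.2.1 only describes and tabulates it, with no VTE-period split.
- JAKi row: it counts the patient if the new factor is also a CV or malignancy factor. Examples are hypertension, diabetes with a diagnosis code, MI, malignancy, reaching 65, or CABG. Annex 11 codes heart failure as I50, I110, I130 and I132 and hypertension as I10–I15, so heart failure under the last three codes is caught too. Heart failure coded I50 alone, other major surgery, new hormonal therapy and a first-coded coagulation disorder are not.
- ADD tables (Sections 9.3.3 and 9.7.2.1): stratification is optional, and the VTE split again uses factors before initiation.
- Continuation and discontinuation after a new VTE factor (Section 9.7.2.4.1): split by VTE period, but without dose.

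A VTE event during induction is not used as an example, because Section 7 recommends that "treatment with tofacitinib be discontinued in patients with suspected VTE", which makes it a question of stopping rather than of dose.

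**3. Which periods carry UC data?** Section 9.2.2 excludes UC patients indexed before May 2019. VTE Period 1 ends on 31 May 2019 (Section 9.2.4). UC therefore has about one month of that 17-month period.

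**4. Scale only.** Let p be the share of UC initiators with a VTE factor before index, and q the share of the rest who acquire a first one in Weeks 1–16. If the biologic-naive and >10 mg shares are equal in both groups, then

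missed / counted = q(1 − p) / p.

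The documents give no q, so q = 1% serves as a unit. For p, the 30% to 80% in Section 9.5 is borrowed, although it concerns any risk factor of interest and not VTE factors in UC.

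- p = 80%: 0.01 × 0.20 / 0.80 = 0.25%
- p = 50%: 0.01 × 0.50 / 0.50 = 1%
- p = 30%: 0.01 × 0.70 / 0.30 = 2.3%

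Of the 2,000 UC initiators projected in Section 9.5, 2,000 × 0.20 = 400 to 2,000 × 0.70 = 1,400 would have no factor before index. Each 1% of q is then 4 to 14 patients over all VTE periods, before restriction to biologic-naive patients above 10 mg. These figures include patients whom the JAKi row catches.

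**The case against.** The strongest reply is that this is structure and not a slip. Table 3 and Section 9.7.2.4.1 agree, the row sits under a pre-initiation heading, and factors arising on treatment have their own block. The sibling rows belong to other outcome families. That stands as far as it goes: a reader might infer an internal contradiction in the VTE analysis, and there is none. But the outcome is maintenance dose, and the on-treatment block records no dose, so the structure leaves the gap open.

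A second reply is that correcting the biologic criterion in the posology row would count the patient there. True, but without a VTE-period split. That split is also worth less in UC than it seems, since Period 1 is almost empty and the usable contrast is Period 2 against Period 3, both after the VTE notification. This limits the point without removing it.

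A third reply is that the SAP may refine definitions (Sections 9.3.1 and 9.7). It may, but the Protocol fixes this window in two places, so it is not a detail left open.

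**Conclusion.** The point holds as a cheap improvement. Against the baseline-to-Week-16 window that the plan uses elsewhere, the count of biologic-naive UC patients with a VTE risk factor on more than 10 mg/day maintenance can only be too low. The amount is unknown and probably small; the scale above depends on a borrowed p, an arbitrary unit of q and equal dosing in the two groups.

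Three stronger readings are not supported.

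- A reader might infer that the comparison of VTE periods is biased. That needs onset during induction, or dosing after it, to differ by period, and nothing in the Protocol shows this. The outcome is only described and tabulated, and the proportion could move either way depending on its denominator.
- A reader might infer that every such patient is lost to the study. The JAKi row catches a good part of the factor list, though not by VTE period.
- A reader might infer a large loss. With q = 10% and p = 30%, the missed share of those flagged to Week 16 would be 0.07 / (0.30 + 0.07) = 19%. With q = 2% and p = 80% it would be 0.004 / (0.80 + 0.004) = 0.5%. The documents support no particular q, so the upper figure is not an estimate.

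**What to change.** In the Table 3 row and in Section 9.7.2.4.1, define at least one VTE risk factor as present from baseline to Week 16. Keep the existing look-backs before index, and use Table 3's on-treatment definitions for Weeks 1–16. State the window in the row itself, because the heading above it says pre-initiation. Report the pre-index version as a sensitivity tabulation.

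The cost is two wording changes and one extra table. No new data are needed, since Section 9.2.3 already ascertains VTE risk factors during follow-up. The non-adherence count may become slightly less favourable. Factors first arising after Week 16 remain uncounted, as in the sibling rows.
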